The methodological shortcomings in the literature mean that only three candidate prognostic factors could be selected for model development from our previous systematic review (22). Therefore, candidate PF selection for our model has been largely based upon evaluation of collinearity, measurement reliability and clinical reasoning. Therefore, it is possible that some important factors have not been considered. As such, only modest performance of this initial model is expected.

It is acknowledged that the proposed prognostic model will assume that participants are independent for each season and utilise the binary outcome of at least one IMI in a season, rather than evaluating time to individual IMI events. This means that we will not account for within-person correlations from season to season. Although this is not fully representative of the real world, because this is a novel area and we are restricted to a relatively small dataset, we have elected to perform the analyses in a more simplistic manner in the first instance. Further, more complex analyses may be conducted in future.

To assess the generalisability of a prognostic model it should be externally validated using data from another location (21, 24) such as a dataset from another comparable elite level football team. Because there is likely to be considerable between-team heterogeneity in PHE processes (16), candidate prognostic factors within our model may not translate externally at this time. There are no immediate plans to externally validate this model. However, depending on the outcome of the model development and PF exploratory studies, it may be possible to conduct a future prospective temporal validation study within the same football club, or external validation study in different population. If feasible, such investigations will require a separate associated protocol.

The current evidence relating to PFs for injury in football is frequently flawed due to issues with the reliability of data measurement, adjustment, dichotomisation and potential diagnostic misclassification, so there is a need for further studies that address these issues (22). Further hypothesis-free exploratory studies that investigate many factors, (including those that are not necessarily biologically plausible) may assist with identification of new factors that may help inform management decisions and monitoring purposes (20).

Furthermore, these types of studies are helpful because new PFs may be used to update a developed model to improve performance (57). We have therefore outlined an associated phase 1 exploratory study to investigate the association between IMIs and other factors from the current dataset using a validated diagnostic outcome classification system, recommended statistical approaches and ensuring where possible, analysis of continuous data remains on the continuous scale to explore linear and non-linear associations.

We anticipate that this investigation will provide a comprehensive evaluation of what is currently possible in terms of using PHE data to predict IMIs at an elite football club, by adhering to transparent reporting procedures and current best practice for model development, validation and exploration of potential PFs. We hope these studies will also identify further research priorities for this novel and potentially valuable area of sports/football medicine research.

DECLARATIONS

Ethical approval and consent to participate

Informed consent was not required; all data were captured from mandatory PHE processes completed through the participant's employment. The anonymity and rights of all players were protected. The use of these data for the current purpose was approved by the Research Ethics Service at the University of Manchester.

Availability of data and materials

An anonymised summary of the dataset that will be generated and analysed during this current study may be available from the corresponding author on reasonable request.

Competing interests

The authors declare that they have no known competing interests.

Funding

The lead researcher (TH) is receiving sponsorship from Manchester United Football Club to complete a postgraduate PhD study programme. This work was also supported by Arthritis Research UK: grant number 20380.

Authors' contributions

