The medical professionals were not blinded to PHE data at the time of diagnosis. These data were not routinely used to inform diagnoses, but instead used to identify functional rehabilitation targets and for benchmarking. Following injury, players completed a rehabilitation programme as directed by club medical staff to enable them to return to training and match participation.

Participants and eligibility criteria

Eligible participants were identified from a review of the PHE database entries during the dates stated above. During any season, participants were eligible for inclusion into the analysis if they: 1) were aged between 16-40 years; 2) had an outfield position (i.e. not a goalkeeper); 3) participated in PHE testing for the relevant season. Participants were excluded from the analysis for any season if they were a triallist player or not contracted to the club at the time of PHE.

Ethics and Data Use

Because all data were captured from the mandatory PHE completed through the participants' employment, informed consent was not required. The anonymity and rights of all players were protected. The football club granted permission to use these data and the use of the data for this study was approved by the Research Ethics service at the University of Manchester.

This study has been registered on ClinicalTrials.gov, with registered number

as

Data extraction

All PHE records from eligible participants were extracted and placed into a separate database. Using the club's electronic medical records system, a further database was generated of all recorded injuries for each season and a manual review of each eligible participant's medical record was undertaken to ensure accuracy. Each injury was categorised according to: 1) contact or non-contact mechanism of injury; 2) injured side; 3) affected body area; 4) injury type i.e. IMI/ligament/tendon/cartilage/contusion or

laceration/bone/concussion/other musculoskeletal injury; 5) muscle group and diagnostic classification if recorded as an IMI. This process allowed an in-house audit of injury incidence and absolute risk evaluation for each injury type for the squad overall and for those who underwent PHE. All IMIs were then extracted and merged with the PHE database of included participants, for each season in which they remained eligible.

Outcome Measures

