The primary outcome measure for both studies will be the occurrence of an initial (index) lower extremity IMI sustained by a participant during a season. Only time-loss injuries will be included; that is, any index lower extremity IMI that occurred during match play or training that resulted in the player being unable to take full part in future match play or training (30). An IMI was confirmed during the injury assessment procedure outlined above, and graded by the club doctor or physiotherapist according to the Munich Consensus Statement for the Classification of Muscle Injuries in Sport (4). This diagnostic classification system is the primary method of muscle injury classification used by the club and has been validated previously (31).

If an index lower extremity IMI occurred, the participant's outcome for the season will be determined and that participant will no longer be considered at risk beyond the time of IMI occurrence. In these circumstances, participants will be included for further analysis at the start of the consecutive season, providing they remain eligible. If participants sustained any upper limb IMI or non-IMI injury type, these will be ignored and the participant will still be considered at risk of a lower extremity index IMI.

Each participant-season will be treated as independent. Eligible participants who were loaned out or transferred to another club throughout that season, but had not sustained an index IMI prior to the loan or transfer will still be considered in the risk set. Participants who sustained an index IMI while on loan will be included for analysis, as outlined above. Any participants who were permanently transferred during a season (anticipated to be very few) will be recorded as not having an IMI event during the relevant season and they will exit the cohort at this point. A sensitivity analysis may be conducted to evaluate the effect of player loans or transfers on the results.

If there are a sufficient number of index IMI outcomes, secondary analyses may be performed, which may include outcomes of hamstring muscle IMIs, functional IMIs (classified as type 1A to 2B), or structural IMIs (classified as type 3 or 4) according to the Munich Consensus Statement criteria.(4)

Sample Size

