Because only 10 PFs will be used in model building, we have defined these candidate PFs *a priori*, (Table 2). Three candidate PFs have known importance based on the results of our previous systematic review so were selected for inclusion (22). All other PFs listed in Table 1

were eligible unless there were >15% missing observations or if reliability (where applicable) was classed as fair to poor (ICC < 0.70) (35). In these cases, the relevant candidate PFs were excluded (Table 3). This was to ensure that only the highest quality data will be used in the analysis, with PFs that would generally be available and routinely measured.

Co-linearity amongst factors within a logistic regression model can cause inaccuracies in standard error and confidence interval estimates (36) so a scatterplot matrix was used to informally assess between-factor correlations for eligible PFs. If PFs were highly correlated, one of the PFs were dropped or new composite PFs were generated and replaced the original factors (highlighted in Tables 2-4). Typically, this occurred where measurements examined both right and left limbs separately; composite factor variables were therefore created for both between-limb measurement differences and the mean of the measurements for both limbs.

Of the remaining eligible PFs, 7 further candidate factors were selected for inclusion, through use of clinical reasoning to identify those with a biologically plausible association with IMI development. The final set of 10 PFs is shown in Table 2.

Table 2: Restricted set of candidate prognostic factors for model development and validation.

Selection method	Candidate Prognostic factor	Composite PF	Measurement unit	Measurement method	Data type	Reliability (if applicable)
Systematic review	Age	No	Years & days	Date of birth	Continuous	N/A
	Frequency of previous muscle injuries within 3 years prior to PHE	No	Count	Medical records	Discrete (treated as continuous)	N/A
	Most recent previous muscle injury within 3 years prior to baseline PHE	No	< 6 months, 6-12 months, > 12 months	Medical records	Categorical	N/A
Clinical reasoning/ data quality	CMJ power	No	Normalised peak force (N/Kg ^{-0.67})	CMJ using force plates	Continuous	Test-retest ICC = 0.92-0.98.(37)
	PROM hip joint internal rotation difference*	Yes	Degrees	Digital inclinometer	Continuous	Intra-rater ICC= 0.90.(38)
	PROM hip joint external rotation difference*	Yes	Degrees	Digital inclinometer	Continuous	Intra-rater ICC = 0.90.(38)

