Discrimination performance is a measure of a model's ability to separate participants who have experienced an outcome compared to those who have not, quantified using the C (concordance) statistic (equivalent to the area under the ROC curve) (23). This index measure will be calculated for the development model, where 1 demonstrates perfect discrimination, while 0.5 indicates that discrimination is no better than by chance alone.

To quantify the degree of optimism due to overfitting, our model will be internally validated using bootstrap re-sampling. This will be conducted as previously outlined (26, 53). The prognostic factor variable selection procedure and model construction will be repeated for 200 bootstrap samples. For each sample, the difference in bootstrap apparent performance (of the bootstrap model in the bootstrap data) and test performance (of the bootstrap model in the original dataset) will be averaged across the 200 samples, to obtain a single estimate of optimism for each performance statistic. Then, to calculate optimism-adjusted estimate of

performance for our new model, the estimates of optimism will be subtracted from the original apparent estimates of performance.

The optimism-adjusted calibration slope will provide a uniform shrinkage factor, which will be applied to all prognostic factor effects in the developed model to adjust (shrink) for overfitting. The intercept of the model will then be re-estimated accordingly. This will then form our final model.

Prognostic factor exploration

All candidate factors eligible for the exploratory study will undergo univariable logistic regression analyses to determine unadjusted associations with IMIs. Candidate PFs will be grouped according to PF type (Table 4) and incorporated into multivariable logistic regression models to determine regression coefficients and odds ratios after adjustment for age, BMI, frequency of previous IMIs and most recent IMI within the 3 years prior to PHE, (which were included as candidates in the original model). During multivariable analysis of the anthropometric candidate factors, BMI will not be included in these models due to collinearity with height and weight factors. Exploration of non-linear associations between candidate factors and index IMI outcomes will be evaluated using a fractional polynomial approach (49). This analysis will allow examination of added prognostic value over and above other factors included in the original model.

DISCUSSION

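### Repeated player-seasons are analysed as independent rows, so ordinary standard errors in the univariable exploratory models will tend to be somewhat too small for factors that are stable within a player

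*Combined protocol and SAP*

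**What the plan says.** Methods, Outcome Measures: "Each participant-season will be treated as independent". The same section says that after an index injury "participants will be included for further analysis at the start of the consecutive season, providing they remain eligible". Under Data extraction, injuries are "merged with the PHE database of included participants, for each season in which they remained eligible". With five seasons pooled (Data sources), a player can contribute one to five rows.

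Statistical analysis, Prognostic factor exploration: "All candidate factors eligible for the exploratory study will undergo univariable logistic regression analyses to determine unadjusted associations with IMIs". No clustered variance, generalised estimating equation or player effect is named. The factors then enter group models adjusted for age, BMI, and the frequency and recency of previous muscle injury (BMI is dropped for the anthropometric group).

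Only one sensitivity analysis is mentioned, it is optional, and it is about something else: "A sensitivity analysis may be conducted to evaluate the effect of player loans or transfers on the results".

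The Discussion acknowledges that seasons are assumed independent and that within-person correlation is not handled. It gives the reasons (a novel area and a small dataset) and leaves more complex analysis for later. It does not say what this does to standard errors or intervals.

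**The concern.** A regression standard error is affected by clustering when both the factor and the outcome are correlated within a player. The plan's own premises suggest that the outcome is. On age and the two muscle-injury history factors it says "Three candidate PFs have known importance based on the results of our previous systematic review so were selected for inclusion". Age advances one year per season, and 3-year injury counts taken in consecutive seasons share two of their three years. A univariable model for another factor omits all of these. One player's outcomes are then positively correlated in that model, even if a full model would leave no residual player effect.

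Height hardly changes from season to season. The other Table 4 factors are exposed only as far as they are stable, which the documents do not report.

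At stake is how certain the unadjusted exploratory odds ratios look. They are meant to point to factors for later studies and for model updating. The plan holds itself to accurate standard errors elsewhere, as its reason for screening correlated factors shows: "Co-linearity amongst factors within a logistic regression model can cause inaccuracies in standard error and confidence interval estimates".

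**Working it through.** **The plan's own figure.** The only computed figure nearby is the expected shrinkage of 0.85 under Sample Size. At an outcome proportion of 0.381 the maximum Cox-Snell R² is 0.735, so a Nagelkerke R² of 25% gives 0.25 × 0.735 = 0.184. Rows: n = 100/0.381 = 262.5. Solving n = p/[(S − 1) ln(1 − 0.184/S)] with p = 10 gives S = 0.845. The figure reproduces within rounding, and this point does not dispute it.

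**Inputs.**
- From the documents: at least 100 events, outcome proportion 0.381 (hence about 263 rows), up to five rows per player.
- Assumed, because the documents do not give them: the number of players, the spread of seasons, the within-player correlation of the factor (rx) and that of the outcome (ry).

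**Formula.** SE multiplier = √[1 + (m − 1)·rx·ry], with m = Σn²/Σn over players' season counts. The chance that a null factor's 95% interval excludes 1 is 2[1 − Φ(1.96/multiplier)].

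| Players | Share with 1/2/3/4/5 seasons (%) | Rows | m |
|---|---|---|---|
| 80 | 16/17/19/20/28 | 262 | 3.90 |
| 105 | 32/24/18/13/13 | 264 | 3.28 |
| 130 | 46/26/14/8/6 | 263 | 2.74 |

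For 105 players: Σn/players = 2.51, Σn²/players = 8.23, and 8.23/2.51 = 3.28.

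**Height-like factor, rx = 0.98.**

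| Players | ry 0.05: multiplier, rate | ry 0.10: multiplier, rate |
|---|---|---|
| 80 | 1.069, 6.7% | 1.133, 8.4% |
| 105 | 1.054, 6.3% | 1.106, 7.6% |
| 130 | 1.042, 6.0% | 1.082, 7.0% |

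Example: √(1 + 2.28 × 0.98 × 0.10) = √1.223 = 1.106.

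**Less stable factors, 105 players, ry 0.05 and 0.10.** At rx = 0.5 the rates are 5.7% and 6.3%. At rx = 0.2 they are 5.3% and 5.5%.

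**Is ry of 0.05–0.10 reasonable?** Take the plan's R² of 25%, a normal linear predictor and no residual player effect. If 30% of the predictor's variance is stable within a player, ry is about 0.055; if 50%, about 0.093; if 70%, about 0.13. Only complete stability gives 0.19. Five of the ten Table 2 factors are between-limb differences and recency changes each season, so complete stability is implausible. At R² of 10% with half stable, ry is about 0.04 and the rate 6.0%.

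**Simulation of the univariable model.** Null height-like factor, 105 players, random player intercept, 2,000 datasets per row (simulation error about 0.5 points):

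| Player SD (log-odds) | Ordinary | Clustered |
|---|---|---|
| 0 | 5.1% | 6.3% |
| 0.5 | 5.6% | 5.1% |
| 0.7 | 6.8% | 5.1% |
| 1.0 | 9.2% | 5.1% |

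Runs indexed by ry agree with the formula. At ry about 0.11 the ordinary rate was 7.7% with 105 players (8.8% with 80, 7.2% with 130), against 5.6–6.0% clustered. At ry about 0.05 it was 5.3–6.4%, close to noise. For a factor that varies freely between seasons, the ordinary rate was 4.0–5.7%, so there was no understatement.

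**Adjusted models.** Table 4 has groups of 2, 20, 5 and 8 factors. With the adjusters, and counting no previous injury as a fourth recency level (an inference), these models have 7, 46, 11 and 14 parameters. In the three small ones, with injury history built from earlier outcomes, ordinary rates were 5–6% and clustered 6–7%. Ordinary rates reached 7–8% (9% with 80 players) only if a residual player SD of 0.7–1.0 was left unabsorbed. In the 46-parameter model ordinary rates were 8.5–10.5% and clustered 10.4–13.2%, so clustering does not help there.

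**The case against.** The strongest reply is that the assumption is disclosed with reasons, and that the affected analysis is preliminary. The univariable models give unadjusted associations. The adjusted models carry the aim of added prognostic value, and no significance rule is set for exploration, so no selection step or stated decision changes. The Discussion also puts the prognostic value of age and previous injury no higher than modest, and for hamstring injury only, whereas the outcome here is any lower-extremity muscle injury. All of this stands, and it keeps the point minor. Disclosure does not settle it, however: the consequence for intervals is not stated, and the appeal to simplicity does not bear on a remedy that leaves the model and the odds ratios unchanged.

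A second reply is that the remedy gains little when the correlation is low. That is also true: with no player effect, clustering moved the rate from 5.1% to 6.3%.

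A reader might go further and expect standard errors 20% too small and intervals excluding 1 in 10% of null cases. Those figures need ry near 0.20. Under the plan's R² that requires an almost wholly stable predictor, or else a sizeable residual player effect for which the documents give no evidence.

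**Conclusion.** The concern holds as a minor one about interval width in the univariable exploratory models. Its direction rests on positive within-player correlation of the outcome, which the plan's premise about age and injury history supports. Its size rests on assumed player numbers and correlations. Under the stated range, standard errors for a height-like factor should be about 5–11% larger (4–13% over 80–130 players), and a null interval excludes 1 in about 6–8% of cases. Appreciably larger effects need a residual player effect, more rows per player, or a more stable predictor than Table 2 suggests.

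Two stronger inferences are not supported. One is that all 35 exploratory factors are affected: those that vary between seasons are not, and the adjusted models are little affected unless a large player effect is left unabsorbed. The other is that internal validation is wrong because the plan says "The prognostic factor variable selection procedure and model construction will be repeated for 200 bootstrap samples" without naming the resampling unit. In simulation the row-level minus player-level calibration slope ran from −0.012 to −0.003 when history was built from prior outcomes, and was positive (0.006–0.012, at most 0.05) when history absorbed the player effect only partly or not at all. With no consistent sign, no error in the shrinkage factor is shown, and no change to the bootstrap or to backward elimination is asked for.

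**What to change.** Keep the simple logistic models and their odds ratios.

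1. Use player-clustered robust standard errors for the univariable exploratory odds ratios.
2. Keep model-based standard errors in the adjusted group models. Show clustered ones only as a sensitivity check in the groups of 2, 5 and 8 factors, not in the 20-factor medical-history group.
3. Report the number of unique players and the distribution of seasons per player, so that readers can judge how much clustering there is.
4. Add a sentence to the Discussion stating the effect of the independence assumption on interval width.

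The cost is a cluster option in the univariable commands and a few sentences of text, with no new data. Intervals for stable factors become slightly wider. With about 100 players the clustered intervals are still not exact: they exclude 1 in about 5–6% of null cases, and sit slightly above 5% even when there is no correlation.

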As this study will retrospectively utilise the available dataset, a formal sample size calculation has not been conducted, as the total sample size and IMI outcomes are already fixed. To maximise power, we have elected to use all data from the 5-season period. This approach agrees with methodological recommendations that data splitting should be avoided, and all available data should be used for model validation (32).

The number of candidate PFs for inclusion in model development will be restricted to be a minimum of 10 events per variable, which is recommended to reduce overfitting and

optimism during development of a logistic regression model (33). Note that ‘variable’ here means a parameter included (or considered for inclusion) in the model that corresponds to one of the PFs. Although data cleaning for the final season is still in progress, we anticipate that the minimum number of index IMIs will be 100, so will restrict to 10 candidate PFs (variables) for inclusion in the model.

Assuming the model will have a modest R Nagelkerke-squared of 25%, then with an anticipated outcome proportion of 0.381, our 10 events per variable restriction corresponds to targeting an expected shrinkage of 0.85, and thus a relatively small amount of overfitting (15%) (34).

Candidate prognostic factors

A complete list of 60 candidate PFs extracted from the PHE dataset is presented in Table 1.

Table 1: Candidate prognostic factors extracted from PHE data

Type of Prognostic Factor	Candidate Prognostic factor	Measurement method	Data type
Anthropometrics	Age	Date of birth	Continuous
	Height	Standing height measure	Continuous
	Weight	Digital scales	Continuous
	Body fat	Skin callipers	Continuous
	BMI	Composite height (cm) and weight (kg)	Continuous
Medical history	Frequency of previous muscle injuries within 3 years prior to PHE	Medical records	Discrete (treated as continuous)
	Most recent previous muscle injury within 3 years prior to baseline PHE	Medical records	Categorical
	Frequency of previous foot or ankle injuries within 3 years prior to PHE	Medical records	Discrete (continuous)
	Most recent previous foot or ankle injury within 3 years prior to PHE	Medical records	Categorical

	Frequency of previous hip or groin injuries within 3 years prior to PHE	Medical records	Discrete (continuous)
	Most recent previous hip or groin injury within 3 years prior to PHE	Medical records	Categorical

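### The 10-events-per-variable rule is defined on model parameters but applied to factors: Table 2 needs at least 11 parameters, so 100 events do not deliver the stated ratio or the 0.85 shrinkage

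*Combined protocol and SAP*

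**What the plan says.** The Sample Size section limits the candidate set to a minimum of 10 events for each variable and explains that a variable "here means a parameter included (or considered for inclusion) in the model that corresponds to one of the PFs". On the event count it says "we anticipate that the minimum number of index IMIs will be 100", and it concludes "so will restrict to 10 candidate PFs (variables) for inclusion in the model". Assuming a Nagelkerke R-squared of 25% and an outcome proportion of 0.381, it adds that "our 10 events per variable restriction corresponds to targeting an expected shrinkage of 0.85", which it describes as about 15% overfitting.

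The first section headed Model development and internal validation repeats the factor count ("Because only 10 PFs will be used in model building"), and the Discussion also frames the limit as factors per 10 outcomes.

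Table 2 lists the 10 factors. Eight are typed continuous. Frequency of previous muscle injury is typed discrete, with a note that it is treated as continuous. Recency of previous muscle injury is typed categorical, with levels "< 6 months, 6-12 months, > 12 months" and no such note. Under Statistical analysis, all 10 factors enter a full logistic model before backward elimination.

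**The concern.** The number of factors equals the number of parameters only if every factor takes one parameter. A three-level categorical factor takes two. The plan chose the parameter, including any parameter merely considered for inclusion, as its unit, so backward elimination does not reduce the count.

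No formal sample size calculation was made because the data are fixed. The events-per-variable ratio and the expected shrinkage are therefore the quantitative case for the size of the candidate set. If the count is wrong, both figures are too favourable for the model that will be fitted, and a reader would take the plan's own rule as met when it is not.

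**Working it through.** **Inputs, all from the Sample Size section or Table 2**

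- Events E = 100 (the anticipated minimum)
- Outcome proportion φ = 0.381, so n = 100 / 0.381 = 262.5 participant-seasons
- Nagelkerke R² = 0.25
- Rule: at least 10 events per parameter

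**Parameter count for Table 2**

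- Eight continuous factors and one count treated as continuous, each entered linearly: 9 × 1 = 9. Fractional polynomials are planned only for the exploratory analysis, so none are counted here.
- Recency, three listed levels: 3 − 1 = 2
- Total: 9 + 2 = **11**
- A player with no muscle injury in the previous three years fits none of the three levels. If such players form a fourth level (an assumption, since the coding is not given), recency takes 3 parameters and the total is **12**.

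**Formula**

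The plan gives no formula. The usual shrinkage criterion for a binary prediction model with P parameters and shrinkage S was used:

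- max R²_CS = 1 − exp{2[φ ln φ + (1 − φ) ln(1 − φ)]} = 0.7353
- R²_CS = 0.25 × 0.7353 = 0.1838
- n = P / [(S − 1) ln(1 − R²_CS / S)], solved for S at the given n

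**The plan's own figure first**

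With P = 10 and n = 262.5, S = 0.845. This is within 0.006 of the stated 0.85, so the stated figure corresponds to 10 parameters. Exactly 0.85 would need n = 273.6, or about 104 events.

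**The Table 2 model at 100 events**

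| Parameters | Events per parameter | Expected shrinkage | Expected overfitting |
|---|---|---|---|
| 10 (as stated) | 100/10 = 10.0 | 0.845 | 15.5% |
| 11 | 100/11 = 9.1 | 0.832 | 16.8% |
| 12 | 100/12 = 8.3 | 0.820 | 18.0% |

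**Events at which the rule would be met**

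- 11 parameters: 110 events, n = 110/0.381 ≈ 289, S = 0.845
- 12 parameters: 120 events, n = 120/0.381 ≈ 315, S = 0.845
- At 110 events with 12 parameters: 9.2 events per parameter, S = 0.833
- For S = 0.85: about 115 events (n ≈ 301) with 11 parameters, or about 125 (n ≈ 328) with 12

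**The case against.** The strongest reply has four parts.

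- **Coding.** The three recency levels are ordered, and a single scored term would bring the model to exactly 10 parameters. The plan does not exclude this in words. But it does not state it either, and Table 2 types the factor as categorical while marking the neighbouring count factor as treated as continuous. On the plan as written, two parameters is the natural reading. A stated one-term coding would be a valid resolution.
- **The 0.85 sentence.** Read literally, it says what a ratio of 10 events per parameter corresponds to, and that is right for any number of parameters: S is 0.845 at 100/10, 110/11 and 120/12. This stands. The error lies in applying the figure to Table 2 at 100 events.
- **The event count.** One hundred is a minimum and data cleaning for the last season was unfinished, so the final count may satisfy the rule. This also stands, but the candidate limit was set at 100, and the documents give no final count.
- **Size and consequence.** Shrinkage drops by 0.013 or 0.025. The assumed R-squared matters more: with 10 parameters and 100 events, a Nagelkerke R-squared of 20% instead of 25% (a value chosen for illustration) lowers S to 0.81. Selection is also repeated in 200 bootstrap samples, and "The optimism-adjusted calibration slope will provide a uniform shrinkage factor" for the coefficients, whatever the parameter count. This is correct, and it confines the problem to the stated justification. It does not make that justification true.

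**Conclusion.** The concern holds. By the plan's own definition, the Table 2 model has at least 11 parameters, and its minimum of 10 events per parameter is not met at the 100 events on which the limit was set. The ratio is 9.1 with 11 parameters and 8.3 with 12. The matching expected shrinkage is 0.832 or 0.820, against 0.845 for the 10 parameters assumed.

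This rests on three conditions: continuous factors entered linearly, recency entered as indicators, and 100 events. The count of 12 also assumes a separate level for players with no recent muscle injury. The error is small and does not invalidate the planned analysis, but a stated figure is wrong and should be corrected.

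**What to change.** In the Sample Size section, count parameters instead of factors. In Table 2, state how recency enters the model and where players with no muscle injury in the previous three years are placed. Then do one of the following:

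1. Restate the figures at 100 events: 11 parameters, 9.1 events per parameter and shrinkage 0.83; or 12 parameters, 8.3 and 0.82. If the cleaned data reach 110 events (11 parameters) or 120 events (12 parameters), say that the rule is met.
2. Hold the candidate set to 10 parameters, by a one-parameter coding of recency or a smaller set of factors, decided before any outcome modelling.

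The cost is a few sentences and one coding statement. Under the first option the stated figures become slightly less favourable. The second gives up either some flexibility in the recency effect or a candidate factor, which is a larger change than the size of the error requires.
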